### 5.2.2 Subsequent Cycles

Subsequent cycles will require study visits within the first week of ivosidenib therapy, but will not require specific evaluations to begin the cycle given the continuous dosing nature of this study. A total of 12 cycles will be administered.

## 5.3 Agent Administration

Ivosidenib will be given orally (PO) once daily (QD) in 28-day continuous cycles. Dosing should occur at approximately the same time each day.

Ivosidenib may be taken with or without food. If it is taken with food, participants should be advised to avoid consuming with a high-fat meal. All participants will be advised to avoid grapefruit and grapefruit products.

---

CONFIDENTIAL

This document is confidential. Do not disclose or use except as authorized.

Ivosidenib tablets should be taken whole; they should not be crushed or chewed. If the participant forgets to take the daily dose, he/she should make up the dose within 12 hours after the missed dose. If more than 12 hours have elapsed or if the dose was vomited, that dose should be omitted and the subject should resume treatment with the next scheduled dose.

Dosing will be escalated as described above in section 5.1.

#### **5.4 Definition of Dose-Limiting Toxicity (DLT)**

Dose-limiting toxicities will be evaluated during cycle 1 (first 28 days) of treatment. Toxicities will be graded and documented according to NCI CTCAE version 4.03.

Non-hematologic DLTs will be defined as any drug-related grade 3 or greater event.

The following exceptions will NOT be considered DLTs in this population:

- grade 3 nausea, vomiting, or diarrhea that lasts  $\leq$  72 hours and responds to medical intervention

Hematologic DLTs will be defined as any drug-related grade 4 neutropenia ( $ANC < 500/\mu L$ ) or thrombocytopenia (platelets  $< 25,000/\mu L$ ) that

- has not resolved to grade 1 or less within 14 days of holding ivosidenib, or
- resolves within 14 days, but then recurs after resuming study drug

Note that anemia is not included as a DLT.

Additionally, febrile neutropenia of any duration, and not due or attributable to the underlying disease or other extraneous causes such as infection, will be considered a DLT.

In addition, any  $\geq$  grade 2 non-hematologic toxicity that the participant finds intolerable or renders the participant unable to take 75% of the assigned doses (e.g. multiple dose interruptions) during the first cycle will be considered a DLT.

Management and dose modifications associated with the above events are outlined in Section 6.

Dosing will proceed within each cohort according to the following scheme.

Number of observed DLTs at a Given Dose Level	Decision Rule
0/3	3 additional evaluable patients will be treated at the dose level. If $\leq 1$ of the 6 treated patients experience a DLT, this is the RP2D. If $\geq 2$ of the 6 treated patients experience a DLT and current dose is dose level 2, de-escalate to dose level 1.
$\geq 2$	De-escalate to dose level 1 if current dose is dose level 2.

CONFIDENTIAL

This document is confidential. Do not disclose or use except as authorized.

1/3	Add 3 more patients at current dose level  a) If 0 of these 3 additional patients experience DLT, current dose is RP2D.  b) If $\geq 1$ of these 3 additional patients experience DLT, then de-escalate to dose level 1 if current dose is dose level 2.
$\leq 1/6$	Current dose is the RP2D

Subsequent (after cycle 1) cycles of ivosidenib will continue, with participants monitored for toxicity and adverse event reporting, but will not be used for DLT evaluation.

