**Treatment may not begin without confirmation from the Coordinating Center that the participant has been registered.**

### **5. TREATMENT PLAN**

#### **5.1 Treatment Regimen**

Ivosidenib will be administered orally every day for 28 consecutive days, defined as a treatment cycle. Appropriate dose modifications are described in Section 6. Reported adverse events and potential risks are described in Section 7. No investigational or commercial agents or therapies other than those described below may be administered with the intent to treat the participant's myeloid malignancy.

---

CONFIDENTIAL

This document is confidential. Do not disclose or use except as authorized.

The starting dose of ivosidenib (AG-120) will be 500mg orally daily. After 3 (or 6) participants are treated at 500mg daily, if this dose is tolerated, then an additional 10 participants will be treated at 500mg daily. If the 500mg daily dose is NOT tolerated in the initial cohort of participants, then the dose will be decreased to 250mg daily. If 250mg daily is tolerated, then an additional 10 participants will be treated at 250mg daily. The only doses studied will be 500mg daily and 250mg daily (the latter, if necessary).

The first cohort will consist of three participants. After the third participant is enrolled to the cohort, enrollment will be put on hold until all three participants have completed the first 28-day cycle. The period for dose-limiting toxicity (DLT) evaluation is the first 28-day cycle. Individual participants must receive at least 50% of the dosing to be DLT evaluable for that cohort. If this criteria is not met, the patient in that dose-escalation cohort may be replaced.

If one of three participants in a cohort experiences a DLT, then an additional 3 participants will be observed at that dose. The recommended phase 2 dose (RP2D) is defined as the highest dose level at which 0 or 1 of six participants experiences a dose-limiting toxicity.

Dose Escalation Schedule	
Dose Level	Dose of Ivosidenib
Level 1	250mg daily
Level 2 – Starting Dose	500mg daily

Once the RP2D is defined, an additional 10 participants will be enrolled at that dose.

If 250mg daily dosing is not tolerated, then the study will end without expansion.

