## 5.2 Pre-Treatment Criteria

### 5.2.1 Cycle 1, Day 1

Treatment may begin at any time between day 30 and day 90 following stem cell transplantation. However, at time of treatment start, it must be ensured that:

- The patient has continued willingness and interest in participating in the study.
- Chimerism studies reveal that  $\geq 70\%$  of blood or bone marrow cells, or of the CD33 expressing fraction, are of donor origin,
- There is no acute graft versus host disease (GVHD), requiring an equivalent dose of  $\geq 0.5\text{mg/kg/day}$  of prednisone within one week of starting ivosidenib, or have escalation of systemic immunosuppression in terms of increase of corticosteroids or addition of new agent/modality within two weeks of starting ivosidenib.
- There is no evidence of relapsed/recurrent/residual disease.
- There is no systemic infection requiring IV antibiotic therapy within 7 days of starting ivosidenib

Prior to the start of ivosidenib administration, the participant must have adequate hematological function, defined as:

- ANC  $\geq 1000/\mu\text{L}$
- Platelets  $\geq 50,000/\mu\text{L}$

and adequate organ function defined as

- Direct bilirubin level  $< 2.0 \text{ mg/dL}$
- AST (SGOT), ALT (SGPT) and Alkaline phosphatase  $< 3x$  institutional upper limit of normal (ULN)
- Presence of congestive heart failure, defined by New York Heart Association (NYHA) criteria as class 3 or 4
- Calculated creatinine clearance  $\geq 40 \text{ mL/min}$  (Cockcroft-Gault formula)

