## 6.7 Hematologic Toxicity

If at any time during ivosidenib dosing, a participant experience a grade 4 thrombocytopenia or grade 4 neutropenia that is possibly, probably or definitely related to ivosidenib, drug must be held until the toxicity resolves to a grade 1 or lower. If it takes more than 14 days for the event to resolve, and it is during the first cycle (28 days) of dosing, the toxicity will be considered to be a DLT (see section 5.4)

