### 6.7.1 250 mg dosing

If the participant was at the 250mg daily dosing level when the toxicity occurred, and it takes longer than 14 days for the event to resolve to  $\leq$  grade 1, then the participant will be taken off treatment and will remain on study only for survival and other outcomes.

If the toxicity takes less than 14 days to resolve to  $\leq$  grade 1, then ivosidenib can be restarted at 250mg daily dosing upon resolution. If the toxicity recurs at grade 4 during the course of the study, then the participant will come off treatment and will remain on study only for survival and other outcomes. If the toxicity recurrence (to grade 4) happens during the first cycle of dosing, then the event will be a DLT.

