### 6.7.2 500 mg dosing

If the participant was at the 500mg daily dosing level when the toxicity occurred, and the toxicity resolves to  $\leq$  grade 1 *after* 14 days, but *before* 28 days (total) have elapsed, then dosing with ivosidenib can resume at the reduced dose of 250 mg daily. If the toxicity recurs at grade 4 during the course of the study, then the participant will come off treatment and will remain on study only for survival and other outcomes.

If the participant was at the 500mg daily dosing level when the toxicity occurred, and it takes *less than* 14 days for the event to resolve to  $\leq$  grade 1, then dosing with ivosidenib can resume at 500mg daily. If the toxicity recurs at grade 4, then dosing will again be held. (This will be a DLT if it occurs during cycle 1). If the toxicity again resolves to  $\leq$  grade 1 within 28 days, then dosing with ivosidenib can resume at the reduced dose of 250mg daily. If the toxicity recurs yet again at grade 4, then the participant will come off treatment and will remain on study only for survival and other outcomes.

A participant who starts at 500mg daily dosing and is subsequently reduced to 250mg daily dosing due to toxicity can potentially increase back up to 500mg daily dosing if subsequent evaluation of the observed toxicity indicates no relation to study drug. Any such re-escalation must have the approval of the principal investigator, [name].

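### A full return to a low but eligible starting count still meets the hematologic DLT definition; separately, sections 5.1 and 13 differ on whether an early-held DLT is counted or replaced

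*Combined protocol and SAP*

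**What the plan says.** **Start criteria.** Section 5.2.1 says: "Prior to the start of ivosidenib administration, the participant must have adequate hematological function". It sets this at ANC 1000/uL or more and platelets 50,000/uL or more, with treatment starting between day 30 and day 90 after transplantation.

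**DLT definition.** Under section 5.4 a drug-related grade 4 neutropenia (ANC below 500/uL) or thrombocytopenia (platelets below 25,000/uL) is a DLT if it "has not resolved to grade 1 or less within 14 days of holding ivosidenib", or if it "resolves within 14 days, but then recurs after resuming study drug". Grading follows CTCAE 4.03.

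**Hold and scoring.** Section 6.7 says "drug must be held until the toxicity resolves to a grade 1 or lower". It scores a DLT under this condition: "If it takes more than 14 days for the event to resolve, and it is during the first cycle (28 days) of dosing". Sections 6.7.1 and 6.7.2 use the same grade 1 target for restart or removal. At 250 mg the participant comes off treatment if "it takes longer than 14 days for the event to resolve to" grade 1; at 500 mg, if that takes less than 14 days, "then dosing with ivosidenib can resume at 500mg daily".

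**Evaluability.** Section 5.1: "Individual participants must receive at least 50% of the dosing to be DLT evaluable for that cohort". A participant who falls short may be replaced. Section 13 defines unevaluable differently: never started, or dropped out or died within 28 days for unrelated reasons without a DLT. It sets no dosing share.

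**Decision.** At most 1 DLT in 6 makes the dose the RP2D. Two or more reject 500 mg, or end the trial at 250 mg.

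**The concern.** There are two separate gaps.

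First, the start criteria and the recovery target use different counts. A participant judged fit to start at platelets 60,000/uL is judged unresolved after falling below 25,000/uL and climbing all the way back to 60,000/uL. For that participant the rule mixes the graft's condition before treatment with the drug's effect. Nothing in the text supplied gives a reason for asking for more than the starting count.

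Second, a hold for cytopenia that begins early leaves little dosing in cycle 1. Section 5.1 would let that participant be replaced even if the DLT definition was met; section 13 would keep the participant and count the DLT. This affects any early-held DLT, whatever the starting count, but the participant in the first gap falls into it too.

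The DLT count alone sets the RP2D. With six participants and a limit of one DLT, a single uncertain classification can change the dose carried forward, or stop the trial at 250 mg.

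**Working it through.** **The plan's own figures.** The plan gives no rejection probability for its 3+3 rule and no cytopenia rates. Its sample size range reproduces: minimum 3 + 3 = 6, maximum 6 + 6 + 10 = 22. So does the ±22% precision for 16 patients (exact 90% interval at 8/16: 27.9% to 72.1%, half-width 22.1%). Neither depends on this point.

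**Step 1: start counts against the recovery target.** The grade 1 floors are an assumption: ANC 1500/uL, platelets 75,000/uL. The gap exists for any floors above 1000 and 50,000.

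| Count at start and again within 14 days | Grade 1 reached? | Meets 5.4 DLT definition? |
|---|---|---|
| ANC 1200 | no | yes |
| ANC 1500 | yes | no |
| Platelets 60,000 | no | yes |
| Platelets 75,000 | yes | no |

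**Step 2: dosing.** Suppose the first held dose is on day 8 and platelets are back at 60,000/uL on day 22. Restart is barred below grade 1, so by day 22 the participant has had 7 of 28 doses (25%), under the 50% in 5.1. How general this is depends on how the DLT sentence of 6.7 is read.
- If the 14-day mark must fall in cycle 1, a hold from day h needs h + 14 ≤ 28, so h ≤ 14. Without restart that leaves at most 13 of 28 doses (46%), and every such DLT is exposed to replacement.
- If only the toxicity must begin in cycle 1, a hold from day 15 onward leaves 14 or more doses when none was missed before. For those cases the 50% rule is met and the conflict disappears.

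**Step 3: the decision rule.** P(reject) = P(2 or more DLTs in 6). At 10%: 1 − 0.9⁶ − 6 × 0.1 × 0.9⁵ = 1 − 0.5314 − 0.3543 = 0.114. Enumerating the two stages of three gives the same value.

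**Step 4: effect of one such participant**, the others having DLT rate p:
- counted as a DLT: 1 − (1 − p)⁵
- replaced: P(Bin(6, p) ≥ 2)
- recovered and evaluable: P(Bin(5, p) ≥ 2)

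| p | Counted | Replaced | Recovered, evaluable |
|---|---|---|---|
| 5% | 23% | 3% | 2% |
| 10% | 41% | 11% | 8% |
| 20% | 67% | 34% | 26% |

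**Step 5: overall size, by assumption only.** Let f be the share starting below the floor, q the share of those with a related grade 4 fall, w the share held by day 14, and s the share returning to at least the starting count but not to grade 1 in time. The counted rate is r = p + (1 − p) × f × q × w × s. Take p = 10% and w = s = 0.5:

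| f, q | r | P(reject) | At least one case in six |
|---|---|---|---|
| 20%, 5% | 10.2% | 11.9% | 1% |
| 30%, 10% | 10.7% | 12.8% | 4% |
| 30%, 20% | 11.4% | 14.2% | 8% |

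Against 11.4% without such cases, the rise is about 0.4 to 2.7 points (from unrounded values). With w = 1 (onset reading) the three become 12.3%, 14.2% and 17.1%. Wider inputs (f 20% to 60%, q 5% to 20%, w = s = 1) give 13.2% to 36.4%. If every such participant is replaced, the figure stays at 11.4%.

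**The case against.** The strongest reply is that this is a deliberate, cautious threshold. A low starting count is never a DLT on its own: 5.4 requires a drug-related grade 4 fall. The rule already forgives grade 4 cytopenia that recovers in 14 days and leaves anemia out. Asking for grade 1 recovery in recent transplant recipients is defensible, and giving no reason is not an error. The grade 1 floors are not printed, the overall effect rests wholly on assumed rates, and the 41% applies only if the case occurs.

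Most of this stands, and it limits the point to a minor one. It does not remove the mismatch: the plan admits these counts as adequate for starting drug and then treats a return to them as unresolved toxicity. Nor is baseline-relative recovery foreign to the protocol, since 6.5 accepts a QTc close to baseline.

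A second reply is that the 50% rule already keeps such participants out of the DLT count. That is one reading, and replacement in 5.1 is optional. Section 13 supports the other. Section 6.5 adds to the doubt by allowing replacement after a cycle 1 discontinuation for grade 4 QTc prolongation, although a drug-related non-hematologic event of that grade is a DLT under 5.4.

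A third reply concerns restart. Allowing 500 mg again at platelets near 50,000/uL, after a related grade 4 fall, is a clinical trade-off. That objection stands, so the restart rules are left out of the fix.

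**Conclusion.** The point holds as a minor one, in two parts. Under the assumed floors, a full return within 14 days to a low but eligible starting count meets the DLT definition. Independently, 5.1 and 13 give different answers on whether a DLT with under 50% of cycle 1 dosing is counted or replaced.

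Two stronger readings are tempting and are not supported. A reader might infer that such a participant is certain to be scored as a DLT; 5.1 permits replacement, so the text does not settle it. A reader might also infer a material bias against 500 mg; the documents give no rates, and the illustrations run from under one point to much larger values depending only on the inputs. The direction is known if the case is counted: towards de-escalation, or towards stopping at 250 mg.

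The firm statement of size is conditional on one case occurring and on a 10% rate in the other participants: rejection at 41%, 11% or 8% according to how that one participant is classified. Confidence is medium, because the floors are assumed and the DLT sentence of 6.7 can be read in two ways.

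**What to change.** 1. In 5.4 and the DLT sentence of 6.7, write: 'resolved to grade 1 or less, or to at least the cycle 1 day 1 count if that was below the grade 1 floor, within 14 days'. Use the count itself, not its grade. The reference is the cycle 1 day 1 CBC, or the one from the previous 7 days that footnote 2 of the study calendar accepts.
2. In 5.1, state that a participant who meets the DLT definition is counted as a DLT whatever share of cycle 1 dosing was received and may not be replaced. State also that a participant held for a cytopenia who recovers by rule 1 and completes the 28-day observation is evaluable. Without this second sentence, someone scored as recovered but not restarted could still be replaced for low dosing. The replacement sentence in 6.5 should be read against the new wording.

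Leave the restart count and restart dose in 6.7 to 6.7.2 to the sponsor's clinical judgement.

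The cost is one phrase in two places and two sentences in 5.1. No new type of data is needed: the 14-day check needs a count by that date whichever target applies. The downside is a slightly less strict DLT rule for participants who start with low counts. Two safeguards remain: recovery below ANC 1000/uL or platelets 50,000/uL cannot qualify, because nobody may start lower, and a recurrence after restart in cycle 1 is still a DLT.

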### **6.1 Acute GVHD**

As mentioned previously, acute GVHD prior to study entry must be clinically stable and requiring  $\leq 0.5$  mg/kg/day of prednisone. For patients who initiate therapy and develop new onset acute GVHD:

- Therapy with topical / local agents such as corticosteroid / tacrolimus cream, oral non-absorbable steroids, ursodiol, etc. are allowed to be used and ivosidenib will continue. Discussion with the Principal Investigator is encouraged.

---

CONFIDENTIAL

This document is confidential. Do not disclose or use except as authorized.

- Systemic therapy  $\leq 0.5$  mg/kg/day of prednisone is allowed to be used with continuation of ivosidenib – i.e. starting 20 mg / day for presumed upper GI GVHD. In no way is this study advocating for the use of a specific dose of steroids for initial therapy of acute GVHD, and treatment of such should not be compromised to continue ivosidenib.
- If requiring systemic steroids  $> 0.5$  mg/kg/day of prednisone, ivosidenib will be held and initial therapy for acute GVHD initiated. If within the next 28 days, the participant is able to improve and be on a stable dose of steroids which is  $\leq 0.5$  mg/kg/day of prednisone (or equivalent), ivosidenib may be restarted at the original dose.
- Participants are forbidden from receiving any “investigational” agents for the treatment of acute GVHD. Discussion with the overall PI is encouraged to define “investigational.” Patients are allowed to participate on clinical trials investigating initial therapy for acute GVHD – i.e. using agents with steroids or agents alone which are not “investigational.”
- If acute GVHD occurs in the dose-escalation cohorts, and this occurs during the first cycle of treatment and patient has taken  $< 14$  days of drug, the participant may be replaced, as DLT evaluation would be impacted.
- Any initiation of systemic therapy beyond steroids for steroid-refractory acute GVHD will result in the participant stopping ivosidenib. Systemic therapy beyond steroids for participants with *steroid-dependent* acute GVHD is allowed and will not result in participant stopping ivosidenib. Discussion with the PI is encouraged.
- For flares of acute GVHD, participants are allowed to increase systemic steroid dose, however, if exceeding 0.5 mg/kg/day of prednisone or equivalent, ivosidenib will be held and the patient will have 28 days to restart if symptoms and steroid requirement guidelines can be met.

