### **6.3 Non-Hematologic Toxicity (except QT prolongation)**

If at any time during ivosidenib dosing, a participant experiences a grade 3 or higher toxicity that is possibly, probably or definitely related to ivosidenib, drug must be held until the toxicity resolves to a grade 1 or lower. If it is during the first cycle (28 days) of dosing, the toxicity will be considered to be a DLT (see section 5.4). In participants with known Gilbert’s disease, grade 3 elevated bilirubin that is possibly, probably or definitely related to ivosidenib would not require study drug hold if the elevation is not due to liver GVHD or veno-occlusive disease. For these participants, study drug must be held for grade 4 elevated bilirubin and resolution/recurrence of toxicity to follow the instructions below in 6.3.1 and 6.3.2.

If and when ivosidenib is held in the midst of a cycle, the cycle day will not change, and once the drug is resumed it will be either on the day that that cycle has progressed to, or if the pause is beyond 28 days of a cycle, the resumption will be called the day 1 of the subsequent cycle.

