### 6.3.2 500 mg dosing

If the participant was at the 500mg daily dosing level when the toxicity occurred, and the toxicity resolves to  $\leq$  grade 1 *after* 14 days, but *before* 28 days (total) have elapsed, then dosing with ivosidenib can resume at the reduced dose of 250 mg daily. If the attributable toxicity recurs at  $\geq$  grade 3 (or grade 4 bilirubinemia in those with known Gilbert's disease – see above section 6.3) during the course of the study, then the participant will come off treatment and will remain on study only for survival and other outcomes.

If the participant was at the 500mg daily dosing level when the toxicity occurred, and it takes *less than* 14 days for the event to resolve to  $\leq$  grade 1, then dosing with ivosidenib can resume at 500mg daily. If the toxicity recurs at  $\geq$  grade 3 (or grade 4 bilirubinemia in those with known Gilbert's disease – see above section 6.3), then dosing will again be held. (This will be a DLT if it occurs during cycle 1). If the toxicity again resolves to  $\leq$  grade 1 within 28 days, then dosing with ivosidenib can resume at the reduced dose of 250mg daily. If the toxicity recurs yet again at  $\geq$  grade 3 (or grade 4 bilirubinemia in those with known Gilbert's disease – see above section 6.3), then the participant will come off treatment and will remain on study only for survival and other outcomes.

A participant who starts at 500mg daily dosing and is subsequently reduced to 250mg daily dosing due to toxicity can potentially increase back up to 500mg daily dosing if subsequent evaluation of the observed toxicity indicates no relation to study drug. Any such re-escalation must have the approval of the principal investigator, [name].

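### The last DLT clause in section 5.4 has no attribution condition, so unrelated post-transplant illness can count toward rejecting a dose, and acute GVHD in cycle 1 has no single classification

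*Combined protocol and SAP*

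**What the plan says.** Section 5.4 has four DLT criteria, all assessed in the first 28-day cycle.

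- General non-hematologic: "Non-hematologic DLTs will be defined as any drug-related grade 3 or greater event", with an exception for short-lived gastrointestinal events.
- Hematologic: "Hematologic DLTs will be defined as any drug-related grade 4 neutropenia" or thrombocytopenia that persists or recurs as specified.
- Febrile neutropenia, provided that it is "not due or attributable to the underlying disease or other extraneous causes such as infection".
- Any grade 2 or higher "non-hematologic toxicity that the participant finds intolerable or renders the participant unable to take 75% of the assigned doses" during the first cycle.

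The first two require a relation to the drug and the third excludes other causes. The fourth does neither.

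Three other sections bear on how a cycle 1 event is classified.

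- Section 5.1: "Individual participants must receive at least 50% of the dosing to be DLT evaluable for that cohort"; a participant who falls short may be replaced.
- Section 6.1 holds ivosidenib when acute GVHD needs systemic steroid above a stated threshold. It adds: "If acute GVHD occurs in the dose-escalation cohorts, and this occurs during the first cycle of treatment and patient has taken" fewer than 14 days of drug, the participant may be replaced, because DLT evaluation would be affected.
- Section 13 calls a participant unevaluable only for never starting, or for dropping out or dying within 28 days without a DLT for reasons unrelated to therapy.

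The dose is accepted with at most one DLT in six and rejected with two or more (5.1, 5.4, 13).

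**The concern.** The primary endpoint in section 13 is the recommended phase 2 dose, and it turns on very few events: two DLTs in six, or two in the first three, reject a dose. Treatment starts between day 30 and day 90 after transplant (5.2.1), and the protocol itself plans for GVHD and infection in that period. A criterion that starts at grade 2 and does not ask about cause can put transplant complications into the dose decision. Because it covers grade 2 and above, it can also bring back an unrelated grade 3 event that the general non-hematologic criterion leaves out.

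The second difficulty is consistency. The same episode of acute GVHD may end as a replacement or as a DLT according to how many doses came before the hold, and the sections do not say which rule governs. In a multi-center trial the primary endpoint would then depend on how each site reads the clause.

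**Working it through.** **1. The plan's own figures.** Section 13 gives 6 to 22 evaluable patients. The shortest path is 3 + 3 = 6 and the longest is 6 + 6 + 10 = 22. The ±22% for a 90% interval with 16 patients matches the exact interval at 8/16, which is 0.279 to 0.721, a half-width of 0.221. Neither figure is at issue. The plan gives no figure for the effect of unrelated events.

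**2. Does the word toxicity already imply a drug cause?** Not in this protocol. Section 6.3.2 allows re-escalation "if subsequent evaluation of the observed toxicity indicates no relation to study drug", and 6.7.2 has the same provision, so an observed toxicity may be unrelated. The secondary objective in 1.3 adds the qualifier ivosidenib-related. Section 6.3 does require attribution, but for a "grade 3 or higher toxicity that is possibly, probably or definitely related to ivosidenib", so it does not reach grade 2.

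**3. The dose counts.** 75% of 28 is 21 doses and 50% is 14. Under 5.5 and the opening of section 6, a hold does not change the cycle day, so missed doses are not made up within cycle 1. For a hold that lasts to the end of the cycle:

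| Doses taken | 5.1 evaluable | 6.1 GVHD replacement | 5.4 below 75% |
|---|---|---|---|
| 0–13 | no, may be replaced | may be replaced | yes |
| 14–20 | yes | not available | yes |
| 21 or more | yes | not available | no |

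In the middle band nothing in 5.1, 6.1 or 13 removes the participant, and the letter of 5.4 points to a DLT. In the first band replacement is optional, and the plan does not say whether 5.4 or the replacement rule takes precedence. The intolerable limb of the clause needs no missed doses at all.

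**4. Illustrative size.** Let p be the drug-related DLT rate and q the proportion of participants with an unrelated event meeting the clause. The documents give neither. Taking the two as independent:

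- counted rate t = 1 − (1 − p)(1 − q)
- P(dose passes) = P(at most 1 of 6) = (1 − t)^6 + 6t(1 − t)^5

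Enumerating the 3+3 branches gives the same result.

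Not every such event need count, because those with fewer than 14 doses may be replaced. Suppose that a hold lasts to the end of the cycle, that it is equally likely after any number of doses from 0 to 20, and that everyone with fewer than 14 doses is replaced. The counting band is then 14 to 20, which is 7 of 21 values, or one third. With a share c counting and the rest replaced, q becomes q′ = qc / (1 − q(1 − c)).

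With p = 10%:

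| q | t, all count | Passes, all count | Passes, half count | q′, one third | t, one third | Passes, one third |
|---|---|---|---|---|---|---|
| 0 | 0.100 | 88.6% | 88.6% | 0 | 0.100 | 88.6% |
| 5% | 0.145 | 78.8% | 83.8% | 0.017 | 0.116 | 85.4% |
| 10% | 0.190 | 68.0% | 78.3% | 0.036 | 0.132 | 81.8% |
| 20% | 0.280 | 46.4% | 65.5% | 0.077 | 0.169 | 73.1% |

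Example for q = 10%, all counting: t = 1 − 0.90 × 0.90 = 0.19, and 0.81^6 + 6 × 0.19 × 0.81^5 = 0.680.

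The one-third column covers only the missed-dose limb. Unrelated events counted through the intolerable limb would lower it.

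**The case against.** The strongest reply concerns GVHD. The protocol gives it its own sections (6.1, 6.2), apart from non-hematologic toxicity (6.3), and its own staging (11.2, 11.3) in place of CTCAE. Section 6.1 speaks of early GVHD as interfering with DLT evaluation, and the hold follows from a steroid threshold. A reader might infer from 5.4 that a GVHD hold is plainly a DLT whatever its cause. The documents do not support that: its status is contradictory. This part of the reply stands.

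It also stands that the figures with every event counted are an upper case for the missed-dose limb, since 5.1 and 6.1 let the earlier events be replaced. No section gives a background rate, and 5.2.1 screens out significant acute GVHD and recent infection needing intravenous antibiotics at drug start.

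The benefit of attribution is limited too. An event that may be related is rated possible (7.2.4), and rash, diarrhea and liver abnormalities are listed drug risks (7.1.2) that overlap with post-transplant illness. The 89% baseline assumes perfect attribution.

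Finally, an all-cause criterion could be deliberate caution, since tolerability is a primary objective (1.2) and GVHD is a secondary one (1.3). The protocol gives no such reason, and the three neighbouring criteria do the opposite. This part does not stand.

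**Conclusion.** The concern holds as a gap in the DLT definition. The last criterion in 5.4 alone has no attribution condition, and neither the use of the word toxicity elsewhere nor the evaluability and replacement rules close the gap. The direction is certain: any unrelated event that is counted lowers the chance that a dose passes. The size is not known. With an assumed 10% drug-related rate and 5% to 20% unrelated qualifying events, the chance of passing is 79% to 46% if all count and about 85% to 73% if one third count, against 89% with none. These figures rest on assumed rates, independence and, for the one-third case, the hold pattern stated in the working.

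A reader might infer that the plan intends to count unrelated illness, or that a tolerable dose is likely to be rejected. The text shows an omission and a conflict between sections, and it supplies no rate from which to call rejection likely.

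**What to change.** In the last criterion of 5.4, state the same attribution condition as for the other DLT criteria, and define it by the categories in 7.2.4 so that all sites apply one threshold. If all-cause counting is in fact intended, the protocol should say so and give the reason.

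Reconcile 5.1, 5.4, 6.1 and 13 so that a cycle 1 hold for unrelated acute GVHD has one stated DLT and evaluability classification, whatever the number of doses taken, and say which rule takes precedence when both a DLT criterion and a replacement rule apply. Which classification to adopt is for the sponsor.

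The cost is a few words in 5.4 and cross-references in the other three sections. Attribution is already assigned to adverse events, so no new data are needed, and the sample size and decision table are unchanged.
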